## **Background/Rationale**

Mood and anxiety disorders are the most common mental illnesses among Canadians, with approximately 4.0 million individuals living with one of these conditions (including children and adolescents). This number is expected to reach over 4.9 million by 2041 (1).

It has been reported that 7.9-8.6% of Canadians would experience a major depression in their lifetime, characterised by a lack of motivation, loss of ability to enjoy favourite activities, difficulty concentrating, feeling of isolation, and having debilitating effects on daily functioning. Meanwhile, 1.1% of Canadians will be affected by Generalised Anxiety disorder (2).

Mental health also carries a financial burden on the individual and the healthcare system. Annual losses at the workplace are estimated to reach \$33 billion, high levels of short-term and long-term disability claims (75% and 79%, respectively) and a very high unemployment rate (70-90%) in individuals with serious mental health (2).

Despite these staggering facts and statistics, stigma is still a barrier to accessing care. In a 2016 survey, 40% of respondents never reached out to healthcare providers, despite experiencing feelings of anxiety or depression (3).

The recent Bloom Program piloted in Nova Scotia revealed the positive patient benefits, when community pharmacists are able to practise to their full scope, in addition to the usual physician care activities that patients with mental health conditions receive (4). These pharmacists were able to demonstrate:

- I. Comprehensive consultations reviewing physical and mental health conditions and medications
- II. Greater collaboration among health providers
- III. Regular patient-centred longitudinal follow-up care and support
- IV. Improved resource access and service navigation

In comparison, Alberta pharmacists practise very similarly, but possess unique opportunities using Additional Prescribing Authority (APA) to prescribe Schedule 1 medications independently and in collaboration with physicians, and have the ability to order and interpret lab results to assist in patient management. This places the Alberta Pharmacist in a prime position to enhance the patient experience and improve their accessibility to care (5, 6).

To justify pursuing this unique opportunity, a literature review of existing pharmacist interventions for patients with major depressive disorder (MDD) and generalised anxiety disorder (GAD) was performed to identify clinical monitoring tools, study duration and monitoring intervals, and pharmacist interventions that affected clinical outcomes.

Of the 163 articles screened, the review included 13 articles. Becks Depression Inventory (BDI), Hopkins Symptom Checklist (SCL-20), and Patient Health Questionnaire (PHQ-9)

were the most common clinical monitoring tools used (31, 23, and 15 percent, respectively). A study period of 6 months with a 3-month monitoring interval was most common.

Interventions that produced clinical improvement included:

- i) Comprehensive patient education and counselling focused on MDD, antidepressant treatment, adverse effect management, and adherence
- ii) Therapy decisions made with the physician
- iii) Regular longitudinal follow-up and support
- iv) Facilitating access to other services (e.g. counsellors, psychiatrist, etc.).

Evaluations regarding pharmacists prescribing in the community pharmacy setting for depression and anxiety have yet to be explored.

The research group are all registered pharmacists in Alberta with BSc or post-grad PharmD level training. All have additional prescribing authority and PraCID for lab ordering and monitoring. Practice backgrounds include hospital, primary care network, and community pharmacy (that operate in close collaboration with physician offices and developed a collaborative clinical practice). In each of these practice settings, we have experience in collaborative management with the patient's primary care providers and/or specialist physicians--ranging from medication education, monitoring, dose adjustments and prescribing actions--for patients with depression and anxiety.

The unique pharmacist prescribing scope in Alberta can build upon and expand beyond medication adherence evaluated by the systematic review and meta-analysis by Reddean et al in 2018--and in addition, directly evaluate pharmacist prescribing, assessment, and monitoring interventions in the community pharmacy setting.

---

## **Purpose**

This is a clinical trial evaluating the experimental intervention of enhanced pharmacist care by pharmacists with additional prescribing authorization (APA) in Alberta, for patients newly diagnosed with Major Depressive Disorder (MDD) and Generalised Anxiety Disorder (GAD).

## **Objectives**

### **Primary objective**

To evaluate the effect (change in the mean PHQ-9 and GAD-7 score) of enhanced pharmacist care by community pharmacists with APA, in monitoring (lab ordering and interpretation, clinical monitoring of MDD and GAD), counselling (patient education), arranging referrals (in collaboration with prescribing physician), and prescribing (dose adjustment, deprescribing, and the addition of adjunctive medication) interventions for patients who have depression and anxiety and are initiated on pharmacotherapy--in comparison to the usual standard level of care conducted by pharmacist and physician.

## **Secondary objectives**

To evaluate the effect of community pharmacist monitoring, counselling, and prescribing interventions on:

### **Clinical:**

- The rate of achieving remission of MDD and/or GAD compared to usual care (using PHQ-9/GAD-7)
- Cognitive and functional impairment related to MDD and/or GAD
- The occurrence of relapse of depression and/or anxiety
- The proportion of patients receiving appropriate and optimised depression and anxiety medication
- Patient complaints and/or experiences of medication-related side effects during treatment for MDD and/or GAD (i.e. GI intolerance, dizziness, weight gain)

### **Process:**

- Number of patients monitored for MDD and GAD while on treatment by community pharmacist
- The impact of the interventions on patient satisfaction and quality of life.
- Assure sustainability by exploring enabling (i.e. pharmacist reimbursement framework) and potential barrier forces (i.e. pharmacist training in managing patients with MDD and GAD)

---

## **Methods**

### **Design:**

Multi-centre randomised controlled trial with patients as the unit of randomization.

### **Setting:**

Community pharmacies in Alberta, Canada—with pharmacist partners (practising pharmacists with APA and PraeID) involved the dispensing, recruitment, follow-up, interventions, engaging both patients and family physicians

---

## **Patients/Population**

### **Inclusion criteria:**

Adults  $\geq$  18 years of age, newly diagnosed with MDD and/or GAD, including:

- Patients starting on medications for the management of adults with MDD (Appendix 1) (7).
- Patients starting on medications for the management of GAD (Appendix 2) (8).

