**Both Groups**

- Indication of medication (i.e. MDD, GAD, or both) will be recorded by the pharmacist partner in the secured study electronic website/database.
- The electronic PHQ-9/GAD-7 questionnaire (Appendix 4) will be sent securely to and completed by the participant at enrollment (month 0) and prior to the participant's in-person scheduled month 6 (final). The questionnaire results will be available to the study investigator and pharmacist participants but linked only to the participant's study ID.
- Participants will receive a pamphlet copy of Alberta Health Services Access Mental Health resource pamphlet "Know Your Addiction and Mental Health Options" which provides information regarding walk-in services, crisis support, and urgent care (10). An equivalent alternative pamphlet can be developed and provided by the study team if this document becomes obsolete or additional update/information is required.

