## **Outcomes:**

### **Primary outcomes:**

The primary outcome is the mean score difference in PHQ-9 and GAD-7 scores from baseline to end of study participation, between the intervention and standard pharmacist care groups.

- Both PHQ-9 and GAD-7 are validated tools for measuring major depressive disorder and generalised anxiety, respectively, in the primary care setting. They are brief and can be self-administered, with similar results yielded with health care provider administered reports. These are desirable given the time restraints and competing demands we anticipate for community pharmacist partners participating in the study(11, 12).
- PHQ-9 scores reflect depression severity; Ranges from 0-27 (Scores: 0-4 none/minimal, 5-9 mild, 10-14 moderate, 15-19 moderately severe, 20-27 severe) (13).
- GAD-7 scores reflect anxiety severity; Ranges from 0-21 (Scores: 0-4 none/minimal, 5-9 mild, 10-14 moderate, 15-21 severe) (13)

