### **Secondary outcomes:**

- Difference in the clinical improvement rates (proportions of participants achieving clinically significant treatment response) between the pharmacist intervention and standard pharmacist care groups from baseline until the end of the study period, using the PHQ-9 and GAD-7 score.
  - For our study, clinically significant treatment response for the PHQ-9 is defined as a reduction in PHQ-9 score by at least 50% from baseline; adequate treatment response for the GAD-7 is defined as a drop in the GAD-7 score by at least 50% from baseline.
- Difference in the proportion of participants with MDD to achieve PHQ-9 score <5 (i.e. remission/no depression) between the pharmacist intervention and standard pharmacist care groups
- Difference in the proportion of participants with GAD to achieve GAD-7 score <5 (i.e. remission/no anxiety) between the pharmacist intervention and standard pharmacist care groups
- Percentage difference in self-reported safety concerns disclosed by participant to pharmacist partner anytime during the study period, between the pharmacist intervention and standard pharmacist care groups:
  - Adverse medication effects (e.g. dizziness, GI intolerance, bleeding, palpitations suggestive of prolonged QTc interval, etc.)

- Suicidal ideation, attempt at suicide
  - Causing withdrawal from study
- 

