### **Sample size and analytical plan:**

#### Sample Size Calculation:

Lindell et al (2018), who evaluated the impact of a psychiatric clinical pharmacists intervention on the change in PHQ-9 and/or GAD questionnaire scores (14), reported a baseline PHQ-9 mean of 15.2 (Standard deviation [SD] of 6.9) and GAD mean of 12.0 (Standard deviation [SD] of 5.8).

Using those reported values and the following assumptions of an 80% power and a 2 sided alpha of 0.05, a sample size of:

- 84 patients (42 in each group) is required to detect a 4.3 point difference in the mean reduction in PHQ-9 scores between the intervention and control group
- 80 patients (40 in each group) are required to detect a 8.3 point difference in the mean reduction in GAD scores between the intervention and control group.

We selected the larger sample size of 84 patients and inflated it by 10%(47 in each group) to account for potential losses to follow-up and withdrawal of consent.

A Data Safety monitoring board will be formed to review adverse events, and data will be sent once recruitment reaches 25% (24 participant) recruitment.

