#### **Analytical Plan:**

All analyses will be conducted on an intention to treat basis. In the case of missing data, a last observation carried forward approach will be used.

Primary outcome will be analysed using ANCOVA, adjusting for all covariates with  $p < 0.25$  between groups

Secondary outcomes will be analysed using ANCOVA, t-test or chi-square test where appropriate, adjusting for all covariates with  $p < 0.25$  between groups.

Trial and Data Management will be done by EPICORE Centre

---

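### PHQ-9 power and the 50% response outcome make no allowance for patients who have only one of the two disorders

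*Protocol*

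**What the plan says.** All points are in the protocol.

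- **Inclusion criteria.** Adults "newly diagnosed with MDD and/or GAD" who are starting a listed medication. One diagnosis is enough. Neither the inclusion nor the exclusion criteria set a minimum PHQ-9 or GAD-7 score.
- **Both Groups.** Every participant answers both scales: "The electronic PHQ-9/GAD-7 questionnaire (Appendix 4) will be sent securely to and completed by the participant at enrollment (month 0") and again before the month 6 visit. The diagnosis is captured too: "Indication of medication (i.e. MDD, GAD, or both) will be recorded by the pharmacist partner". No use of it in the analysis is stated.
- **Primary outcomes.** "The primary outcome is the mean score difference in PHQ-9 and GAD-7 scores from baseline to end of study participation", compared between the groups, with no restriction by diagnosis.
- **Secondary outcomes.** Response is a fall of at least 50% from baseline on each scale, for participants generally. Remission is limited by diagnosis: "Difference in the proportion of participants with MDD to achieve PHQ-9 score <5", and likewise GAD-7 below 5 among those with GAD.
- **Sample Size Calculation.** "84 patients (42 in each group) is required to detect a 4.3 point difference in the mean reduction in PHQ-9 scores", with SD 6.9, 80% power and two-sided alpha 0.05, inflated to 47 per group. For GAD the stated difference is 8.3 points with SD 5.8 and 40 per group. No diagnostic mix is given.
- **Analytical Plan.** "All analyses will be conducted on an intention to treat basis", and "Primary outcome will be analysed using ANCOVA", adjusted for covariates that differ between groups at p < 0.25.

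**The concern.** Read together, these sections put a patient with GAD alone into the PHQ-9 primary analysis and a patient with MDD alone into the GAD-7 one. A patient without MDD may start low on PHQ-9 and have little room to improve. If so, the average PHQ-9 difference over all randomised patients is smaller than the difference in patients with MDD. The sample size uses a single 4.3-point effect for everyone, so any such dilution comes straight out of the power.

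The response outcome has a further problem that needs no assumption about case mix. A 50% fall with no baseline floor cannot be evaluated at a baseline of 0, and a change from 2 to 1 counts as a clinically significant response. Patients without the matching disorder are those most likely to start that low. The protocol ties remission to the diagnosis but not response, although both are read from the same scales in the same list of outcomes.

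**Working it through.** **Inputs from the protocol.** PHQ-9 difference 4.3, SD 6.9, 42 evaluable per group, two-sided alpha 0.05. GAD difference 8.3, SD 5.8, GAD baseline mean 12.0.

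**Inputs assumed.** f is the share of participants with MDD. r is the effect in patients without MDD as a fraction of the planned effect. The protocol gives neither, so f runs from 90% to 50% and r is 0 or 0.5. The SD is held at 6.9.

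**Step 1: reproduce the plan's figure.** The two-sample t-test at 4.3/6.9 needs 41.4, that is 42 per group or 84 in all, as stated. 42/0.9 = 46.7, that is 47 per group, also as stated. Power at 42 per group is 80.6%. The smallest difference with 80% power at 42 per group is 4.27 points, or 99% of 4.3. There is almost no slack.

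**Step 2: dilute the PHQ-9 effect.**

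Mean difference = 4.3 × [f + (1 − f) × r]

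Standard error = 6.9 × √(2/42) = 1.506

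Power comes from the t-test with noncentrality equal to the mean difference divided by 1.506. For example, at f = 0.8 and r = 0 the difference is 4.3 × 0.8 = 3.44, the noncentrality is 2.28 and the power is 62%.

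| Share with MDD | Difference, r = 0 | Power, r = 0 | Difference, r = 0.5 | Power, r = 0.5 | Power if restricted to MDD (42f per group, 4.3 points) |
|---|---|---|---|---|---|
| 90% | 3.87 | 72% | 4.09 | 76% | 76% |
| 80% | 3.44 | 62% | 3.87 | 72% | 71% |
| 67% | 2.88 | 47% | 3.59 | 65% | 63% |
| 50% | 2.15 | 29% | 3.23 | 56% | 50% |

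All-participant power is below 80% in every row.

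**Step 3: would restriction help?** Restricting to MDD keeps the full effect but loses patients. Equating the restricted and all-participant power gives a break-even r of 47% at a 90% share, 46% at 80%, 44% at 67% and 40% at 50%. Restriction gains power only when the effect in patients without MDD is below that.

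**Step 4: baseline adjustment.** Suppose the baseline score is in the ANCOVA and correlates 0.5 with the final score (assumed). The SD becomes 6.9 × √(1 − 0.25) = 5.98, and power with no dilution is 90%. With r = 0 it is 74% at an 80% share, 59% at 67% and 37% at 50%. With r = 0.5 it is 84%, 78% and 69%.

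**Step 5: GAD-7.** At 8.3 points and SD 5.8, 42 per group and no effect in patients without GAD, power is 99% at a 67% GAD share and 90% at 50%. It reaches 80% only at a share of about 43%. The 8.3-point difference needs 9 per group, not 40. A difference of 12.0 − 8.3 = 3.7 does give 40. At 3.7 points, with r = 0, power would be 64% at an 80% share, 49% at 67% and 30% at 50%.

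**The case against.** Analysing everyone as randomised on both scales is valid and unbiased for the population enrolled; choosing that or a by-diagnosis comparison is partly a choice of estimand. Nothing in the protocol says that patients without MDD gain nothing on PHQ-9. The intervention is general (medication changes, counselling, referral for psychotherapy), and several PHQ-9 items, such as sleep, fatigue and concentration, need not be near zero in a patient with GAD. The 4.3 points may already come from a mixed population, since the source study is described as using PHQ-9 and/or GAD scores. The 6.9 is a baseline SD, and ANCOVA could do better.

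Much of this stands. It is why the loss is given as a range and why restricting the primary analysis is not put forward as the obvious remedy: at r = 0.5 it equals or lowers power. It does not remove the point. Half the effect in patients without MDD still leaves PHQ-9 power at 76% or less on the plan's own SD. Baseline adjustment is not assured, because covariates enter only if they differ between groups at p < 0.25; where it applies, it restores 80% in some of these settings but not all.

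A reader might infer that 80% power requires every patient to have both disorders. The protocol does not support that: PHQ-9 power depends on the share with MDD and GAD-7 power on the share with GAD, so a trial of patients with MDD alone would keep its full PHQ-9 power. A reader might also infer that power is lost on both scores. On the stated 8.3 points it is not; that would follow only if about 3.7 was meant, and the mismatch between 8.3 and 40 per group is a separate error.

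**Conclusion.** The point holds for PHQ-9 power and for the response outcome.

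**Power.** The 84 evaluable patients give 80% PHQ-9 power only if essentially all of them have MDD, or if those without MDD benefit equally on PHQ-9. With zero to half of the 4.3 points in patients without MDD, power is 62-72% at 80% MDD, 47-65% at 67% and 29-56% at 50%. This rests on an assumed case mix and residual effect, an SD of 6.9, no gain from baseline adjustment, and 4.3 points being the effect in patients with MDD. The protocol does not settle any of these.

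**Response.** The rule as written is undefined at a baseline of 0 and credits trivial changes, and its population does not match that of the remission outcomes. No assumption is needed for this.

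That the primary analysis must be restricted to the matching diagnosis does not follow. It is a trade-off that turns on whether the effect in non-matching patients is below about 40-47% of the planned one.

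**What to change.** 1. Define PHQ-9 response among participants whose recorded enrolment indication includes MDD, and GAD-7 response among those whose indication includes GAD, in line with the remission outcomes. Because no minimum score applies even then, add a line on how a baseline of 0 is counted.
2. In the sample size section, say that 80% PHQ-9 power assumes essentially all 84 evaluable patients have MDD or that those without it benefit equally on PHQ-9. Give power over a range of case mix and residual effect, as in the table above, and say whether the 4.3 points come from a mixed population.
3. Record the indication before randomisation. Pre-specify a by-diagnosis analysis of each primary score beside the all-randomised one, with patients analysed as randomised within diagnosis, and state before unblinding which is primary and why.

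The cost is some outcome wording and a less favourable power statement. The indication is already collected, so no new data item and no extra patients are needed. These changes make the power statement accurate; they do not by themselves restore 80% power.

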**Exclusion criteria:**

- Pregnancy
  - Non-Alberta residents
  - Unwilling or unable to participate in regular follow-up visits
  - Unwilling to participate/sign consent form
  - $\geq 2$  suicide attempts per year
  - Severe, psychotic, and catatonic depression
  - Current substance abuse, intoxication, addiction, or withdrawal requiring acute care management
  - Patients diagnosed with comorbid anxiety disorders other than GAD, including: panic disorder, agoraphobia, specific phobia, social anxiety disorder, obsessive-compulsive disorder, posttraumatic stress disorder
  - Patients diagnosed with comorbid depressive disorder other than MDD, including: depressive disorder due to another medical condition (e.g. hypothyroidism, MS, OSA, Parkinsons, stroke, TBI, Vitamin B12 insufficiency, Huntington disease, adrenal insufficiency, mononucleosis, systemic lupus erythematosus), adjustment disorder with depressed mood
  - Patients diagnosed with concurrent ADHD, bipolar disorder, schizophrenia and schizoaffective disorder
- 

**Recruitment:**

Potential participants will be identified and approached by the pharmacist partners (pharmacists with APA and PraCID) if they are picking up or dropping off their prescription for a medication listed in Appendix 1 and 2.

Medication indication will be verified with the patient for the treatment of diagnosed MDD and/or GAD (and if additional verification is required--collateral from physician, Netcare consult note, or pharmacy record).

As part of the standard of pharmacist practice (as outlined in the Alberta College of Pharmacist Standards of Practice for Pharmacist and Pharmacy technicians [9]), a patient is clinically assessed for pharmacotherapy appropriateness by the pharmacist partner. This process is performed by the pharmacist partner and is the initial screen to determine if the patient meets any inclusion or exclusion criteria.

Determined by the pharmacist partner, if a patient meets the inclusion criteria for the study and does not meet any exclusion criteria, the patient will be asked if he/she wants to participate in the study and be provided with a formal invite letter to review.

If the patient agrees on participating, he/she will be asked to sign a written informed consent form. After signing the consent form, the patient will be enrolled in the study and randomised as a study participant using the secured electronic study website/database (developed by EPICORE and secured at the University of Alberta research office).

The participant's physician will receive the notification letter for physicians, from the pharmacist partner, to inform him/her that the participant has agreed to participate in the study. Should the physician refuse to have the participant participate in the study, the participant will not be enrolled into the study.

Should the participant decline recruitment into the study, they will continue to receive the same level of pharmacist care as outlined in the Alberta college of pharmacists standards of practice (9).

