### **Randomization**

Multiple pharmacies are involved in participant enrollment--therefore, once informed written consent is obtained from the patient, the patients will be randomised by stratified randomization using a blocking factor to assign participants to either intervention or usual care groups.

Each participant will be assigned a unique identifier number and group allocation for the duration of their participation in the study--this unique identifier and allocation will also be communicated to and recorded by the pharmacy partner in the participant's patient profile to ensure consistency of the degree of pharmacist interventions described by the group the participant is allocated to.

The participant will be sent a secured electronic link (to the contact number or email they provided in the written consent form) that will include the participant's unique identifier and group allocation and the electronic version of the PHQ-9/GAD-7 questionnaire tool to complete and submit electronically. If the participant is unable to provide a means for the electronic link to be sent, the questionnaire tool can be completed with the pharmacist partner in person prior to their scheduled in-person/telehealth pharmacist meetings.

The study data (i.e. the participant's submitted electronic questionnaire tool results) will be sent directly to a centralised and secured website/database to ensure allocation concealment for the investigational team.

The participant questionnaire scores are available to the pharmacist partner via a secured electronic website/database prior to their scheduled in-person/telehealth meeting with the pharmacist partner.

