**1) Patient Assessment:**

- Recording participant scores from the combined PHQ-9/GAD-7 questionnaire tool (Appendix 4) completed by the participant, which includes:
  - PHQ-9 (Patient Health Questionnaire 9-item), a multipurpose instrument for screening, diagnosing, monitoring and measuring the severity of depression
  - GAD-7 (Generalised Anxiety Disorder 7-item)
- If determined clinically relevant by the pharmacist partner will assess:
  - appearance, current mood, sleeping patterns, mental health, medical history, social history, family history, relationships with others, suicidal ideation, previous suicide attempts or hospitalizations, current employment status.

2) Pharmacist-initiated prescribing dose adjustment, medication change to different medication, deprescribing, or prescribing adjunctive add-on medication, to achieve clinical response and/or remission of MDD and/or GAD and establish appropriate cognitive/functional status as per CAMAT guidelines (7, 8).

3) Provide regular communication updates with the patient's family physician after each contact with the patient (via fax or electronic charting).

4) Providing medication counselling and educational support to the participant.

5) Identification of adverse drug effects, drug interactions, or severe deterioration (i.e. suicide attempt)

6) Interim telephone/telehealth follow-up conducted by the pharmacist partner since the last in-person follow-up & a minimum of 1-2 weeks after the last in-person follow-up that involved a dose adjustment, prescribing of adjunctive medication, or discontinuation of therapy. (Note: a telephone follow-up does not replace the scheduled in-person/telehealth follow-up).

7) Collaborate with physician to arrange referral to psychologist, psychiatrist, counsellor or social worker for psychotherapy

Should the participant from the interventional group drop out or complete the 6 month study period, they will be offered to continue with similar interventional care or standard pharmacist care but no data will be collected since their dropout or following study completion.

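### Randomisation follows patient consent alone, yet a physician refusal makes the patient not enrolled: as written, a randomised patient can be removed, against the intention-to-treat statement

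*Protocol*

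**What the plan says.** Two sections of the protocol give the trigger for randomisation, and they agree. Recruitment: "After signing the consent form, the patient will be enrolled in the study and randomised as a study participant". Randomization: "once informed written consent is obtained from the patient, the patients will be randomised by stratified randomization using a blocking factor". Neither mentions the physician.

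The next paragraph of Recruitment brings the physician in: "The participant's physician will receive the notification letter for physicians, from the pharmacist partner, to inform him/her that the participant has agreed to participate". The letter has no date. The refusal rule follows directly: "Should the physician refuse to have the participant participate in the study, the participant will not be enrolled into the study". It has no time limit.

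The Analytical Plan states: "All analyses will be conducted on an intention to treat basis". It adds: "In the case of missing data, a last observation carried forward approach will be used".

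Two further statements show who can know the arm. On allocation, Randomization says: "this unique identifier and allocation will also be communicated to and recorded by the pharmacy partner in the participant's patient profile". Item 3 of the intervention list reads: "Provide regular communication updates with the patient's family physician after each contact with the patient". The Control Group section lists no such updates.

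**The concern.** A person who was enrolled and randomised at consent cannot later be someone who was never enrolled. If sites follow the text in the order given, a refusal arrives when an allocation already exists, and the natural reading of the refusal rule is that the person then leaves the trial. Intention to treat is meant to prevent removal after randomisation.

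The harm would be greatest if refusals were related to the arm. The pharmacist who sends the letter knows the allocation. Intervention activity begins at enrolment (month 0), and the physician is updated after each contact. With no deadline, a physician could object after learning from an update that the pharmacist is adjusting treatment. A control patient's physician has no corresponding prompt. The groups left for analysis would then no longer be those that randomisation formed.

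**Working it through.** **1. The order of steps.**

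| Step | Where | What it waits for |
|---|---|---|
| Enrolment and randomisation | Recruitment; Randomization | Patient's written consent only |
| Physician letter | Recruitment, next paragraph | No date given |
| Physician refusal | Recruitment, same paragraph | No deadline given |
| Analysis | Analytical Plan | Intention to treat |

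There are two readings.
- *Refusal can come after randomisation.* The refusal rule then un-enrols a randomised person, against intention to treat.
- *Refusal was meant to come before randomisation.* The consent-only trigger is then wrong in both sections, and sites that follow it will randomise too early.

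The text needs correcting under either reading.

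**2. The plan's own sample size.** Inputs from Sample Size Calculation: difference 4.3, SD 6.9, two-sided alpha 0.05, power 80%.
- Normal approximation: n = 2 × (1.960 + 0.842)² × 6.9² / 4.3² = 40.4, so 41 per arm.
- Two-sample t-test: 41.4, so 42 per arm and 84 in total, as stated.
- Inflation: 42 / 0.90 = 46.7, so 47 per arm, as stated. The reasons named for the 10% are loss to follow-up and withdrawal of consent. Physician refusal is not among them.

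**3. Power if refused patients are dropped.** The refusal rate v is not given, so the values below are assumptions. Power is for a two-sample t-test with equal rates in both arms.

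| v | 47 × (1 − v) per arm | Power | 47 × 0.9 × (1 − v) per arm | Power |
|---|---|---|---|---|
| 0 | 47 | 0.85 | 42.3 | 0.81 |
| 5% | 44.7 | 0.83 | 40.2 | 0.79 |
| 10% | 42.3 | 0.81 | 38.1 | 0.77 |
| 20% | 37.6 | 0.76 | 33.8 | 0.71 |

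The left pair fits the plan better, because carrying the last observation forward keeps participants who are lost but have a baseline score. The right pair also deletes the planned 10%. If refusals fall in the intervention arm only and the 10% is deleted as well, power is 0.80 at v = 5% and 0.79 at v = 10%.

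**4. Bias if refusals fall in one arm only.** Suppose a fraction v of the arm is removed, and the removed patients' mean PHQ-9 change differs by D from that of the patients who stay. The full-arm mean is (1 − v) × m + v × (m + D) = m + vD, where m is the mean of those who stay. Dropping them therefore shifts the arm mean by vD. Both v and D are assumptions.

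| v | D = 2 | D = 4 |
|---|---|---|
| 5% | 0.1 | 0.2 |
| 10% | 0.2 | 0.4 |
| 20% | 0.4 | 0.8 |

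As a share of the 4.3-point target this runs from 0.1 / 4.3 = 2% to 0.8 / 4.3 = 19%.

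**The case against.** The strongest reply is that the refusal sentence may itself have been meant as a gate before enrolment. The letter is undated, and the order of paragraphs is weak evidence for the order of events. A reader might infer that vetoed patients definitely are removed after randomisation. The protocol does not establish that. It establishes only that its statements on timing cannot all be followed.

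Three further objections carry weight.
- **Analysis set.** No section says that refused patients leave the analysis. That is inferred from their being treated as not enrolled, and the exact analysis set may be defined in a statistical analysis plan that is not shown. Such a plan could not, however, correct the recruitment sequence that sites follow.
- **Dependence on arm.** A reader might infer that physicians refuse knowing the arm, and that the intervention arm is left with easier cases. The letter is described only as reporting the patient's agreement. An update could precede a refusal only if the letter were late or the refusal slow. The exclusion criteria already remove severe, psychotic and catatonic depression from both arms. The mechanism is possible but not documented.
- **Power.** A reader might infer that refusals leave the trial underpowered. From 47 per arm with the planned carry-forward rule, refusals of 5% or 10% in both arms still leave power of about 0.83 or 0.81. Power falls below 0.80 at these rates only if the 10% loss is also deleted.

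The inconsistency in the recruitment sequence survives all of these.

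**Conclusion.** The point holds as an inconsistency that should be corrected. Randomisation is tied to patient consent alone, while a physician refusal is said to prevent enrolment, with no waiting step and no deadline. Applied literally, this permits exclusion after randomisation, against the intention-to-treat statement.

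Arm-related selection is a conditional risk. It requires that refusals come after allocation, that they relate to the arm, and that refused patients differ in outcome. Under the assumed values the shift is 0.1 to 0.8 PHQ-9 points, and it would be zero if refusals were rare or unrelated to both arm and outcome. The effect on power is small at assumed rates of 5% to 10% and is not a reason to change the sample size.

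**What to change.** In Recruitment and Randomization, send the physician letter at consent. Release randomisation only after the physician agrees, or after a short no-objection period whose length is stated. A refusal in that time is then a screen failure, and no randomised patient is lost to it.

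In the Analytical Plan, state that anyone randomised stays in the intention-to-treat set as allocated if a refusal arrives later, and that such refusals are reported by arm.

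The first change costs a short delay between consent and randomisation. The second needs more than one sentence. The Intervention Group, Control Group and Continuity of care plan sections all say that no data are collected after dropout, so any data collection after a late refusal must be reconciled with them. Without it, a retained patient who has only a month-0 score would count as unchanged under the carry-forward rule. Settling the response before randomisation keeps such cases few.
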